### 9.3.3 Potential confounders/risk factors

A broad range of risk factors and potential confounders, related to the offspring, father and mother, will be considered in the multivariable analysis. These include, but are not limited to, demographic and clinical characteristics and concomitant medications. The final choice of confounders will depend on the availability of data, clinical relevance and model fit.

The list of potential risk factors and potential confounders for NDD and CM are summarised below in Table 2, Table 3, Table 4 with further detail found in Annex 3. Additional Information. Factors listed as exclusion criteria for the comparative, sensitivity and exploratory objective analyses and the potential confounder list (Table 4) are omitted from the potential risk factors tables (Table 2, Table 3).

**Table 2: Potential risk factors for NDD**

Mother	Father	Offspring

 
• Age
 
• Obesity (12 months look back from LMP2) 
 
• Smoking (12 months look back from LMP2 and DP)
 
• Substance abuse (12 months look back from LMP2 and DP)
 
• Alcohol abuse (12 months look back from LMP2 and DP)
 
• Schizophrenia, schizotypal and delusional disorders (ever)
 
• Affective Disorder (ever)
 
• Neurotic Disorder (ever)
 
• Rubella (DP)
 
• CMV (DP)
 
• Diabetes (ever) & Gestational Diabetes (DP)
 
• Any concomitant medications associated with valproate-indicated psychiatric conditions (12 months look back from LMP2 and DP) 
 
• Any concomitant medications associated with neuropsychiatric adverse effects (12 months look back from LMP2 and DP) 
 
	
 
• Substance Abuse (12 months look back from LMP2)
 
• Affective Disorders (excluding bipolar and mania) (ever)
 
• Schizophrenia, schizotypal and delusional disorders (ever)
 
• Neurotic Disorder (ever)
 
• Any concomitant medications associated with valproate-indicated psychiatric conditions (12 months look back from LMP2) 
 
• Any concomitant medications associated with neuropsychiatric adverse effects (12 months look back from LMP2) 
 
	
 
• Sex
 
• Foetal Alcohol syndrome
 
• Fragile X Syndrome
 
• Congenital CMV
 
• Congenital Rubella
 
• Lejeune/ cri du chat syndrome
 
• Tuberous sclerosis
 

 In addition to recognised risk factors, any co-medications received (including other psychoactive treatments received) during the exposure periods described in section 9.3.1, will be investigated and adjusted for in the analysis using a polypharmacy index.

NDD: Neurodevelopmental disorders; LMP2: Last Menstrual Period + 2 weeks; DP: during pregnancy; CMV: Cytomegalovirus

Omitted from this list are

- risk factors that are exclusion criteria for comparative, sensitivity and exploratory objective analyses:
  - mother: history of epilepsy and NDD,
  - father: history of NDD,
  - child: exposure to AEDs and diagnosis of epilepsy after birth
- paternal factors listed in Table 4.

**Table 3: Potential risk factors for CM**

Mother	Father	Offspring

 
• Age
 
• Obesity (12 months look back from LMP2)
 
• Smoking (12 months look back from LMP2 and DP)
 
• Alcohol abuse (12 months look back from LMP2 and DP)
 
• Substance abuse (12 months look back from LMP2 and DP)
 
• Diabetes (ever)
 
• Gestational diabetes (DP)
 
• Rubella (DP)
 
• Varicella (DP)
 
• Toxoplasmosis (DP)
 
• Herpes Simplex virus (DP)
 
• CMV (DP)
 
• Folate deficiency (DP)
 
		
 
• Congenital Rubella
 
• Congenital Varicella
 
• Congenital CMV
 
• Congenital Herpes Syndrome
 
• Congenital toxoplasmosis
 
• Foetal Alcohol Syndrome
 

CM: Congenital Malformations; LMP2: Last Menstrual Period + 2 weeks; DP: during pregnancy; CMV: Cytomegalovirus

Omitted from this list are

- risk factors that are exclusion criteria for comparative, sensitivity and exploratory objective analyses:
  - mother and father: congenital malformations including chromosomal disorders,
  - mother: teratogenic drugs
- paternal factors listed in Table 4: potential confounders

**Table 4: Potential confounding variables by outcome**

Outcome	Father
NDD, including ASD	
 
• Age
 
• Bipolar Affective Disorder and mania (ever)
 
• Calendar year of conception of offspring
 

CM	
 
• Age
 
• Calendar year of conception of offspring
 

NDD: Neurodevelopmental disorders; ASD: Autism Spectrum Disorder; CM: Congenital Malformations

**Paternal age.** Multiple epidemiological studies suggest a relationship between advanced paternal age at conception, and adverse neurodevelopmental outcomes (19,20) and congenital malformations (21–23) in offspring. This has been particularly noted with regard to increased risk for autism. ‘Paternal Age’ will be considered a confounding variable a priori, for both outcomes.

**Paternal Bipolar Affective Disorder and Mania.** Valproate is indicated in the treatment of epilepsy, mania and migraine (24). Moreover, children of parents diagnosed with mood disorders including mania have been shown to present with increased risk of neurodevelopmental outcomes. For these reasons, in this study, paternal bipolar affective disorder and mania will be considered as potentially confounding the effect of paternal valproate use on the development of neurodevelopmental disorders in offspring.

**Maternal epilepsy.** There is an increased risk of NDD, including ASD, and CM, in the offspring of female patients with epilepsy (25,26). However the high risk of NDD, including ASD in the offspring of female patients with epilepsy may be due to foetal exposure to AED medication in utero (2), including valproic acid. Offspring from women with epilepsy will only be included in the descriptive analyses of the sample from source population following data extraction, and excluded from the comparative, sensitivity and exploratory objective analyses.

**Maternal exposure to AEDs,** especially during pregnancy, is known to be a strong risk factor for NDD, including ASD, and CM in offspring (2). Offspring maternally exposed to AEDs (including valproate), *in utero* or three months before conception, will be described and then excluded from the comparative, sensitivity and exploratory objective analyses. Person-time exposed will be classified to take into account intensity of drug exposure during the 3-months pre-conception and pregnancy risk window (see Figure 6 and Figure 7) using the longitudinal K-means clustering (R package kml) algorithm (15) and applied to the relevant analysis. This method allows for a more precise description of exposure of mothers to drugs. More details on the application of the methodology are reported in section 9.3.1.3.

**Maternal, paternal and offspring exposure to drugs other than AEDs** (including other psychoactive treatments received) during the exposure periods described in section 9.3.1, will be considered using a polypharmacy index.

The plausibility of polypharmacy as a confounding variable or risk factor is based on evidence that polypharmacy is associated with harms including adverse drug effects, drug-to-drug interaction, hospitalization and mortality. Furthermore, there is evidence that psychoactive drugs of other therapeutic class that may often be prescribed in combination with AEDs may be a risk factor for the NDD (such as antidepressants – (6)).

There is currently no consensual definition of polypharmacy. In this study a continuous variable will be defined reflecting medication count as the basis for the exclusive definition of polypharmacy and to describe the medication burden based on the cumulative number of prescribed medications from other therapeutic class (i.e. other than AEDs) to which a relevant individual is exposed within an interval of interest. For the father, this interval would be the 3-months period prior to conception. For the mother the interval would be based on available data on medications prescribed in the three months prior to conception and during gestation period.

Paternal polypharmacy would be a potential confounding variable included in the PS for NDD analysis. Maternal polypharmacy would be considered as a risk factor. For the child, polypharmacy after birth will not be considered as a risk factor in this study. This is because of the high potential of reverse causality; for example there is evidence that children with aberrant behaviours irrespective of diagnosis of NDD are more likely to receive psychotropic polypharmacy. Published literature also suggests subjects with ASD may also have comorbid psychiatric conditions requiring psychotropic treatment and in this regard it is not always possible to define temporality (27–29).

For the CM analysis the polypharmacy score will not be calculated because offspring whose parents were exposed to teratogens (risk factor when considered as maternal exposure and confounders when considered as paternal exposure), associated with maternal exposure in the literature, were already excluded from the CM cohort for the purpose of the comparative analyses (see section 9.3.3.2).

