5. *Simple pairwise comparison valproate vs lamotrigine and valproate vs levetiracetam in monotherapy.* Valproate, lamotrigine and levetiracetam are medications with similar indications but that may be systematically prescribed for different type of epilepsy (such as valproate for genetically determined epilepsy and lamotrigine for focal onset epilepsy) and potentially other indications (lamotrigine might be prescribed for bipolar disorder and levetiracetam is not). Moreover, they were licensed in different periods (levetiracetam since 2000; lamotrigine since early 1990s; and valproate since 1967 to

treat epilepsy and since 1995 to treat bipolar disorder) resulting in systematic different in the treated populations. With the objective to evaluate if there is a differential effect of using one or the other comparator, a supplementary analysis will be provided to contrast valproate paternal exposure to separately lamotrigine and levetiracetam paternal exposure for the purpose of both NDD and CM outcome:

- a. Describe the characteristics of mother, father and offspring for both the primary and secondary outcome cohort and separately for paternal monotherapy exposure to individual AEDs (valproate or lamotrigine or levetiracetam).
  - b. Investigate the risk of NDD, including ASD, in offspring paternally exposed to valproate (monotherapy), compared to lamotrigine (monotherapy) treatment at the time of conception.
  - c. Investigate the risk of NDD, including ASD, in offspring paternally exposed to valproate (monotherapy), compared to levetiracetam (monotherapy) treatment at the time of conception.
  - d. Investigate the risk of CM, in offspring paternally exposed to valproate (monotherapy), compared to lamotrigine (monotherapy) treatment at the time of conception, in Norway and Denmark only.
  - e. Investigate the risk of CM, in offspring paternally exposed to valproate (monotherapy), compared to levetiracetam (monotherapy) treatment at the time of conception, in Norway and Denmark only.

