6. *Comparison of the PS-weighted model with the traditional covariate adjustment model:* A Cox PH regression model will be used to estimate the HR of NDD, including ASD, with 95% CI (using offspring's calendar age in years as the underlying timescale) in offspring paternally exposed to valproate monotherapy within 3 months prior to LMP2 date compared to the reference group comprised of offspring paternally exposed to lamotrigine or levetiracetam (composite monotherapy) in the same time period. A logistic regression model will be used to estimate the OR of CM with 95% CI in offspring paternally exposed to valproate monotherapy within 3 months prior to LMP2 date compared to the reference group comprised of offspring paternally exposed to lamotrigine or levetiracetam (composite monotherapy) in the same time period. The list of confounders to be included is reported in Table 4. Within-family dependencies introduced by multiple offspring per father will be accounted for using sandwich estimators. Different results are expected because two different set of variables will be used for the adjustment due to the inclusion of risk factors in the PS model to improve efficiency; (c) noncollapsibility of the two models (46,50–52) (“the conditional OR or HR does not equal the marginal OR or HR in the presence of non-null treatment effect, even in the absence of confounding and effect modification” (52)).
7. *Effect of paternal exposure to valproate on NDD in offspring exposed and unexposed to AEDs after birth, and/or diagnosed with epilepsy.* As reported in section 9.3.3.1 the neurodevelopmental effects of postnatal exposure to AEDs and/or diagnosis of epilepsy on risk of NDD are not completely understood. Therefore, in the primary analysis such children are excluded. A sensitivity analysis will be conducted to explore the impact on the risk of NDD, including ASD, in offspring paternally exposed to valproate (monotherapy), compared to lamotrigine or levetiracetam (composite monotherapy) treatment at the time of conception will be performed by including these offspring. Offspring exposure to AEDs and diagnosis of epilepsy between birth and the exit date will each be considered time dependent, and thus allowed to take place at any time during the follow-up period. However, after the first dispensation of AEDs, the offspring will be considered exposed until the exit date.

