8. *Validation of the assumption that individuals are exposed to one DDD per day.* WHO DDD is the assumed average maintenance dose per day for a drug used for its main indication (i.e. epilepsy for valproate, lamotrigine and levetiracetam) in adults. This does not necessarily reflect the recommended or Prescribed Daily Dose. Therapeutic doses for individual patients and patient groups will often differ from the DDD as they will be based on individual characteristics (such as indication, age, weight, ethnic differences, type and severity of disease) and pharmacokinetic considerations. A comparison (ratio) between the distribution of estimated treatment durations (expected) and time between prescriptions (observed) will be provided with the caveat that this will necessarily be affected by the DDD methodology approximation. In order to partially overcome this limitation, this comparison will be provided separately for patients with and without an indication of epilepsy, as epilepsy is the main indication for the medicines at study therefore the indication used by WHO to estimate DDD. It is expected that the use of WHO DDD will be a better approximation of the observed treatment duration among patients with a diagnosis of epilepsy, with a ratio closer to one than for other indications. The distribution of estimated treatment durations (expected) will be compared to the distribution of time between prescriptions (observed), *separately for lamotrigine, levetiracetam, valproate and for patients with and without an indication for epilepsy*, using the following formulas:

Observed time between prescriptions for patient i is

$$\sum_{j=1}^{k-1} \text{days} (\text{prescription}_{j+1} - \text{prescription}_j)$$

where k is the number of prescriptions for each patient.

Expected treatment duration for patient i is

$$\frac{\sum_{j=1}^{k-1} n. \text{pkg in prescription}_j * n. \text{dosage unit in each pkg}}{\text{WHO DDD}}$$

where k is the number of prescriptions for each patient.

The ratio of Observed over Expected for patient i is

$$\begin{aligned} \sum_{j=1}^{k-1} \text{days} (\text{prescription}_{j+1} - \text{prescription}_j) / \frac{\sum_{j=1}^{k-1} n. \text{pkg in prescription}_j * n. \text{dosage unit in each pkg}}{\text{WHO DDD}} &= \\ &= \sum_{j=1}^{k-1} \frac{\text{days} (\text{prescription}_{j+1} - \text{prescription}_j) * \text{WHO DDD}}{n. \text{pkg in prescription}_j * n. \text{dosage unit in each pkg}} \end{aligned}$$

The ratio for the population

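### Paternal epilepsy is named in no confounder or risk-factor table, so nothing requires the analyses to adjust for it, and sensitivity analysis 6 as written cannot.

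*Protocol*

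**What the plan says.** Table 4 in section 9.3.3 gives the confounders. For neurodevelopmental disorders (NDD) they are paternal age, bipolar disorder or mania, and calendar year of conception. For CM they are paternal age and "Calendar year of conception of offspring" only. The text under the table explains the psychiatric entry: it cites the indications of valproate, with epilepsy named first, adds that children of parents with mood disorders have raised neurodevelopmental risk, and concludes that "paternal bipolar affective disorder and mania will be considered as potentially confounding the effect of paternal valproate use".

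The father column of Table 2 (NDD) holds psychiatric diagnoses, substance abuse and two co-medication groups. The father column of Table 3 (CM) is empty. The note under Table 2 lists factors left out because they are exclusion criteria; for the father this is a history of NDD, not epilepsy.

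Section 9.7.5, item 5, says the study drugs "may be systematically prescribed for different type of epilepsy (such as valproate for genetically determined epilepsy and lamotrigine for focal onset epilepsy"), and possibly for other indications. Item 6, the covariate-adjusted comparison with the PS-weighted model, is closed: "The list of confounders to be included is reported in Table 4". Item 8, the check on the defined daily dose (DDD) assumption, already uses the epilepsy indication: "this comparison will be provided separately for patients with and without an indication of epilepsy".

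**The concern.** Confounding by indication needs a factor that influences drug choice and is associated with the outcome. The protocol supplies the first link for epilepsy: it says prescribing may follow epilepsy type and other indications. It also applies indication-based reasoning to mania, and then does not apply it to epilepsy.

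If paternal epilepsy, or its type, is related to offspring NDD or CM and is unevenly distributed between valproate and lamotrigine/levetiracetam fathers, part of the estimated effect would reflect the father's disease. Sensitivity analysis 6 would give no warning: agreement between it and the PS-weighted result says nothing about a variable that one model excludes and the other need not contain. The gap is wider for CM, where no indication variable is listed and the polypharmacy index is not calculated.

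**Working it through.** **Plan's own figure.** The protocol gives no figure for this bias. The nearest yardstick is the HR of 2.0 in section 9.5 (4% reference risk, two-sided 5%, 80% power, 1178 offspring). It reproduces closely: Freedman's formula gives 71 events, and 71 / 0.06 (mean of 4% and 8%) = 1183. The point does not rest on this number.

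**Where paternal epilepsy appears.**

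| Place | Paternal epilepsy named? |
|---|---|
| Table 4, NDD | No (age, bipolar/mania, calendar year) |
| Table 4, CM | No (age, calendar year) |
| Table 2, father column | No |
| Table 3, father column | Empty |
| Exclusions noted under Tables 2 and 3 | No |
| Annexes 3D and 3E, father rows | No |
| Annex 3F (CM) | No father rows |
| Annex 3A and Table 19 | Epilepsy listed as an indication, code G40 undivided |
| Section 9.7.5, item 8 | Yes, as a split in the DDD check only |

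**What each adjusted analysis is bound to.**
- PS models (section 9.7.3.2.3) consider the section 9.3.3 confounders as reported in the literature, and section 9.3.3 says its list is not exhaustive. Epilepsy may enter. It need not, and a candidate is taken forward only if its single association with the outcome is above 1.1 or below 0.9.
- Outcome models (sections 9.7.3.2.1 and 9.7.3.2.2) may add covariates not retained in the PS if prognostically important variables are imbalanced. This is optional.
- Sensitivity analysis 5 separates the two comparators but adds no epilepsy covariate.
- Sensitivity analysis 6 uses Table 4 only, so epilepsy is excluded.

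**Illustrative size.** For an unadjusted binary factor with prevalence p1 in valproate fathers and p0 in comparator fathers, and risk ratio RR for the outcome, the spurious risk ratio under no true effect is

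(1 + p1(RR − 1)) / (1 + p0(RR − 1)).

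With a 4% reference risk the HR is close to this. All three inputs below are assumptions.

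| RR | p1 = 50%, p0 = 30% | p1 = 60%, p0 = 20% |
|---|---|---|
| 1.3 | 1.15/1.09 = 1.06 | 1.18/1.06 = 1.11 |
| 1.5 | 1.25/1.15 = 1.09 | 1.30/1.10 = 1.18 |
| 2.0 | 1.50/1.30 = 1.15 | 1.60/1.20 = 1.33 |

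A harsher grid (RR 1.5 to 3, prevalence from 50% vs 20% to 80% vs 10%) runs from 1.25/1.10 = 1.14 to 2.60/1.20 = 2.17; only its most extreme cell passes 2.0. Swapping the prevalences between the groups inverts the first table, giving 1.09/1.15 = 0.95 down to 1.20/1.60 = 0.75. The direction is therefore set by the assumptions.

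**The case against.** The strongest reply is that the PS, which drives the primary HR, is not tied to Tables 2 to 4. The list is declared open, literature-based confounders are to be considered, imbalanced covariates may enter the outcome models, and the final list may sit in an analysis plan that is not shown. This stands. A reader might infer that PS weighting cannot remove the confounding; the text does not support that. What remains is that nothing requires epilepsy to be included, and that sensitivity analysis 6 is closed.

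Other parts of the design bear on the same problem. The comparators are active drugs in monotherapy, chosen to limit disease-severity bias (section 9.3.1). Secondary objective 3 describes fathers treated for epilepsy and other indications, so imbalance could become visible. Exploratory objective 6 looks at exposure-discordant siblings with familial liability in mind, though only descriptively. For NDD, the psychiatric, co-medication and polypharmacy variables partly stand in for indication. These soften the gap without adjusting for epilepsy, and the stand-ins are not listed for CM.

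The outcome link is also thin. Section 9.3.3 reports raised risk in offspring of mothers with epilepsy and says the NDD part may be due to in utero drug exposure. Section 9.3.3.1 expects a correlation between epilepsy and NDD, but in the child. Nothing in the protocol states that paternal epilepsy raises offspring risk.

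**Conclusion.** The point holds as an omission with a cheap remedy. Paternal epilepsy meets the protocol's own reasoning on indication, is not an exclusion criterion, has a codelist, and is already used in one sensitivity analysis. Yet no list names it, sensitivity analysis 6 cannot adjust for it, and the CM lists contain no indication at all. Section 9.9.2 mentions residual confounding only in general terms.

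Four stronger readings are not supported:
- **That this is the main confounding.** This is a judgement; section 9.7.5 says only that prescribing may differ in this way.
- **That valproate against levetiracetam carries the same imbalance as valproate against lamotrigine.** The protocol assigns levetiracetam no epilepsy type and says only that, unlike lamotrigine, it is not prescribed for bipolar disorder.
- **That the HR is biased upwards by a known amount.** The range of 1.06 to 1.33 rests wholly on assumed risk ratios and prevalences. It is well short of the HR of 2.0 used for sizing, but could matter when a smaller HR is interpreted.
- **That epilepsy type is ready to use.** Table 19 carries G40 undivided, and the protocol does not show that sub-codes were extracted or are adequately recorded.

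**What to change.** - Add paternal epilepsy, defined as any G40 record before LMP2 (yes/no), to Table 4 for both NDD and CM.
- Include it in both PS models whatever the result of the outcome-association screen, and in sensitivity analysis 6.
- Report its balance between exposure groups before and after weighting.
- Add one sensitivity analysis restricted to fathers with a G40 record.
- Add epilepsy type from the G40 sub-codes where these are available and adequately coded. Otherwise name confounding by epilepsy type as a specific limitation in section 9.9.2, because a yes/no variable does not address type.

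The cost is one or a few extra PS parameters and one further analysis on a smaller cohort. Long-standing epilepsy may be under-recorded, notably in Norway, where Table 5 gives patient-registry linkage only from 2008; this should be stated alongside the results.
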